7.2.2 Exclusion criteria related to the current knowledge of Sanofi compound

- E 24. Any of the following laboratory abnormalities at the Screening visit (identified by the central laboratory):

- E 25. Female adolescent patients of childbearing potential, unwilling to use, if adequate for age, an effective method of contraception (eg, birth control pills, double-barrier contraception, etc) during treatment and for up to at least 3 months following the last dose (as defined in the informed consent form (ICF) and/or in a local protocol addendum/amendment), and/or who are unwilling or unable to be tested for pregnancy;

Notes: Abstinence may be a possible option depending on local rules and/or regulations; however, if a female patient is abstinent but becomes sexually active during the course of the study, she must be willing to use an effective method of contraception. Sexual counseling will be provided for adolescent patients.

- E 26. Positive pregnancy test at Screening or Baseline

- E 27. Breast-feeding female adolescent patients.

7.2.3 Additional exclusion criteria during or at the end of Screening

- E 28. Patient/parent/legal guardians who has withdrawn consent before enrollment

8 STUDY TREATMENTS

8.1 INVESTIGATIONAL MEDICINAL PRODUCT(S)

Investigational Medicinal Product

Sarilumab, anti-IL-6R mAb (anti-interleukin 6 receptor alpha subunit monoclonal antibody).

Formulation

Sarilumab drug product will be provided at 175 mg/mL in an aqueous buffered vehicle, pH 6.0. It will be supplied in a 5 mL vial filled by 2.7 mL of sarilumab with an extractable volume of 2.0 mL.

Route(s) of administration:

Sarilumab will be administered subcutaneously in the abdomen or thigh when self-injections or also in upper arm (lateral side) by a professional or a non-professional caregiver. It is preferred that SC injection sites be alternated between the 4 quadrants of the abdomen (except the navel or waist area) or the thigh (front and side).

For patients receiving Dose Regimens 1 or 2 (q2w), injections will be performed by a professional caregiver at the site during the 12-week core treatment phase of the study. For patients receiving Dose Regimen 3 (weekly injections), arrangements must be made for qualified site personnel or home nurse to administer IMP for the doses that are not scheduled to be given at the study site. For the extension phase of the study, if the patients or the parent(s) or the legal guardian(s) or the caregiver(s) are willing and able to perform the injections, the home injection will be permitted. In those cases, the training will be required and provided to prepare and administer IMP starting at Visit 10 (Week 8) at the core treatment phase. This training must be documented in the patients' study file. The patients or the parent(s) or the legal guardian(s) or the caregiver(s) are allowed to administer the injections **under observation/supervision** by the Investigator(s) or the delegate(s) at Visit 10 (Week 8), Visit 11 (Week 10), and Visit 12 (Week 12) before the allowance for home injection at the extension treatment phase.

On days when the patient has a study visit, the IMP will be administered following clinical procedures and blood collection. Diaries will be provided to record information pertaining to these injections; these diaries will be kept as source data in the patients' study file. If the caregiver is unable or unwilling to administer IMP, arrangements must be made for qualified site personnel to administer IMP for the doses that are not scheduled to be given at the study site.

Dose regimen

Sarilumab should be administered q2w or qw. However, the sarilumab administration window of ± 3 days for Dose Regimen 1 and 2 Cohorts, and ± 1 day for Dose Regimen 3 Cohort is permitted per protocol to accommodate exceptional circumstances, eg, laboratory test result pending,

ongoing adverse event (AE), patient scheduling difficulty except the Visit 5 (Day 8). There is no administration window at Visit 5 (Day 8). There will be only ± 1 day of administration window for patients enrolled in all dose cohorts at Visit 7 (Week 2) and ± 1 day of administration window for Dose Regimen 3 Cohort or ± 2 for Dose Regimen 1 and 2 Cohorts at Visit 8 (Week 4).

Note that an overdose (accidental or intentional) with the IMP is defined as at least twice the dose during an interval of less than 11 days for q2w administrations and less than 6 days for weekly administration (see [Section 10.4.4.1](#)).

The following sarilumab dose is to be administered q2w or qw:

Dose Regimen 1:

- Group A (≥ 30 kg and ≤ 60 kg): 2 mg/kg q2w
- Group B (< 30 kg and ≥ 10 kg): 2.5 mg/kg q2w.

Dose Regimen 2:

- Group A (≥ 30 kg and ≤ 60 kg): 3 mg/kg q2w
- Group B (< 30 kg and ≥ 10 kg): 4 mg/kg q2w.

Dose Regimen 3:

- Group A (≥ 30 kg and ≤ 60 kg): 2 mg/kg qw
- Group B (< 30 kg and ≥ 10 kg): 2.5 mg/kg qw.

Dose modification

The dose (mg) to be administered to patients will be calculated at Baseline. The dose and corresponding volume of drug product will remain the same throughout the course of the 12-week core treatment phase of the trial regardless of change in patient's body weight. In the extension phase, the patient's weight will be measured at each visit and the dose will be adapted to the increase of weight only if the calculation shows a need for dose increase. The dose will be capped at 150 mg and 200 mg for Dose Regimen 1 and 3 and Dose Regimen 2, respectively. Volumes to be injected depending on patient's weight are further detailed in [Appendix B](#).

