6.3 DURATION OF STUDY PARTICIPATION

6.3.1 Duration of study participation for each patient

Total duration of study (per patient) is expected to be up to 166 weeks for patients enrolled in the dose-finding and second portions and up to 106 weeks for patients enrolled in the third portion:

- Up to 4 weeks + 3 days screening (up to 31 days)
- 12-week core treatment phase

- Up to 144-week extension phase for patients enrolled in the dose-finding and second portions and up to 84-week extension phase for patients enrolled in the third portion
- 6-week post-treatment follow-up.

For all visits, a time frame of ± 3 days for Dose Regimen 1 and 2 Cohorts and ± 1 day for Dose Regimen 3 Cohort is acceptable using Day 1 as reference except for

- For Visit 3 (Day 3), Visit 4 (Day 5) and Visit 5 (Day 8), no visit window is allowed where PK sampling occurs
- Visit 6 (Day 12) ± 1 day for all applicable dose regimen cohorts
- Visit 7 (Week 2) ± 1 day for all dose regimen cohorts
- Visit 8 (Week 4) ± 2 days for Dose Regimen 1 and 2 Cohorts and ± 1 day for Dose Regimen 3 Cohort.

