10 STUDY PROCEDURES

10.1 VISIT SCHEDULE

It is preferred that all study visits take place in the morning when fasting blood samples are required. A non fasting condition could overestimate LDL/triglycerides value which will affect notification of related AEs/AESIs. To permit reliable results, fasting status for at least 8 hours is required for each visit at which fasting lipids laboratory tests will be performed. If the test is performed centrally, both the duration of fasting and the reason of no fasting will be reported in central laboratory data base.

For all visits, a time frame of ± 1 day for Dose Regimen 3 Cohort and ± 3 days for Dose Regimen 1 and 2 Cohorts is acceptable using Day 1 as reference except for:

- Visit 3 (Day 3), Visit 4 (Day 5), and Visit 5 (Day 8), no visit window is allowed where PK sampling occurs
- Visit 6 (Day 12) ± 1 day for all applicable dose regimen cohorts
- Visit 7 (Week 2) ± 1 day for all dose regimen cohorts
- Visit 8 (Week 4) ± 2 days for Dose Regimen 1 and 2 Cohorts; and ± 1 day for Dose Regimen 3 Cohort.

The previous laboratory testing needs to be reviewed by the Investigator or Investigator's designee based on local guidelines before IMP administration and dispense. The results of the evaluation will be recorded on the appropriate e-CRF pages.

Patients who discontinue the study treatment prematurely will be assessed using the procedure planned for the EOT (Visit 27) These patients will be asked to return for the EOS assessment 6 weeks after the EOT visit (Visit 28/EOT+ 6 weeks). For patients who discontinue the study treatment during the 12-week core treatment phase (at or before Week 12), there will be an additional PK assessment 2 weeks after the EOT visit (Visit 88/EOT + 2 weeks) (the additional PK assessment is only applicable for patients in the dose-finding and second portions). For patients who discontinue the study treatment permanently during the 12-week core treatment phase, these patients should return for the protocol scheduled visits for the planned assessments without study medication administration until Visit 12.

Screening Period (Day -28 to Day -1 + 3 days, maximum up to 31 days)

10.1.1 Visit 1: Screening (Day -28 to Day -1, up to 31 days) for all patients

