10.4.4 Guidelines for reporting adverse events of special interest

10.4.4.1 Reporting of adverse events of special interest

For AESIs, the Sponsor will be informed immediately (ie, within 24 hours), as per the SAE notification instructions described in [Section 10.4.3](#) and [Table 7](#) even if not fulfilling a seriousness criterion, using the corresponding pages in the e-CRF (to be sent) or screens in the e-CRF. The following is the list for AESIs for this study:

- Clinically significant infections including:
 - Opportunistic infections (refer to [Appendix I](#)) (Note: Candidiasis – only systemic and/or extensive mucocutaneous cases of candidiasis)
 - Active/latent tuberculosis or initiation of medications for suspected tuberculosis
- Anaphylaxis fulfilling the criteria in the [Appendix H](#)
- Gastrointestinal
 - Perforation
 - Diverticulitis
- The following laboratory abnormalities:
 - Alanine aminotransferase increase leading to permanent discontinuation
 - Grade 4 neutropenia (>10 days after the initial IMP administration) or any neutropenia leading to permanent discontinuation
 - Thrombocytopenia leading to permanent discontinuation
- Pregnancy (adolescent):
 - Pregnancy occurring in a female patient included in the clinical trial (as well as pregnancy occurring in a female partner of a male subject entered in a study with IMP) will be recorded as an AESI in all cases and reported to the sponsor immediately (within 24 hours of knowledge). It will be qualified as an SAE only if it fulfills the SAE criteria.
 - In the event of pregnancy in a female participant, IMP should be discontinued.
 - Follow-up of the pregnancy in a female participant or in a female partner of a male participant is mandatory until the outcome has been determined, or as permitted according to applicable local regulations.
- Symptomatic overdose with IMP
 - An overdose (accidental or intentional) with the IMP is an event suspected by the Investigator or spontaneously notified by the patient and defined as at least twice the

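### Visit windows counted from Day 1, with no stated minimum dosing interval, allow two in-window every-other-week doses 8 to 10 days apart, which Protocol 8.1 counts as an overdose

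*Protocol*

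**What the plan says.** - **Visit windows.** Protocol 6.3.1 allows ±3 days for Dose Regimens 1 and 2 (q2w) and ±1 day for Dose Regimen 3 (weekly); this "is acceptable using Day 1 as reference except for" certain early visits. Among these, Week 2 is ±1 day for all cohorts, and Week 4 is ±2 days for q2w. Section 10.1 repeats the rule, and the core-phase flow chart (1.2.1) prints the windows against study days.
- **Where doses are given.** Section 8.1 says that for q2w patients "injections will be performed by a professional caregiver at the site during the 12-week core treatment phase of the study". The visit date is therefore the dose date.
- **Administration window.** Section 8.1 gives the same widths for dosing and says that the window "is permitted per protocol to accommodate exceptional circumstances". It names no reference day and states no minimum interval.
- **Overdose.** The same section defines it as "at least twice the dose during an interval of less than 11 days for q2w administrations and less than 6 days for weekly administration". SAP 2.4.3.2 agrees in substance. Protocol 11.4.1.2 words it differently, as two or more doses in under 11 (q2w) or 6 (weekly) calendar days.
- **Reporting.** Section 10.4.4.1 describes an overdose as "an event suspected by the Investigator or spontaneously notified by the patient". A symptomatic overdose is an event of special interest; one without symptoms is reported as an ordinary adverse event.
- **Trough samples.** Protocol 11.4.4 and SAP 2.4.4 exclude a q2w trough sample taken under 11 or over 17 days after the previous dose.

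**The concern.** When each window is fixed to Day 1, the widths of two neighbouring windows add up. A dose three days late followed by one three days early loses six days from a 14-day interval, although neither dose breaks the schedule. The protocol then has two rules that disagree about the same pair of doses: the visit schedule permits it and the overdose definition catches it.

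Three things are at stake. A child may receive two full doses closer together than the authors seem to have intended. A site that followed the schedule may have to report an overdose. A pre-dose sample at the second dose may drop out of the trough summary. Every third-portion patient is dosed q2w (flow chart 1.2.2.3, footnote on dosing), so this applies to current enrolment and not only to the dose-finding cohorts.

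**Working it through.** **Inputs.** From Protocol 6.3.1 and 8.1: q2w core doses on Days 1, 15, 29, 43, 57, 71 and 85, with windows of 0, ±1, ±2, ±3, ±3, ±3 and ±3 days. Overdose threshold: under 11 days (q2w), under 6 days (weekly).

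**The plan's own thresholds.** 14 − 3 = 11 and 7 − 1 = 6. Each is the nominal interval less one general window, which is the shortest gap if the window runs from the previous dose.

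**Gaps with windows counted from Day 1.** If the earlier dose is x days off its nominal day and the later dose y days off, the gap is 14 + y − x. It is under 11 when y − x ≤ −4.

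| Interval (q2w) | Possible gap (days) | Pairs under 11 days | If both dose days count |
|---|---|---|---|
| Day 1 to Week 2 | 13–15 | 0 of 3 | 0 |
| Week 2 to 4 | 11–17 | 0 of 15 | 0 |
| Week 4 to 6 | 9–19 | 3 of 35 | 1 of 35 |
| Weeks 6–8, 8–10, 10–12 (each) | 8–20 | 6 of 49 | 3 of 49 |

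- Week 4 to 6: the pairs (x, y) are (2, −3), giving 9 days, and (2, −2) and (1, −3), giving 10 days.
- Each later interval: one pair gives 8 days (3, −3), two give 9 and three give 10.
- Last column: if the calendar days in Protocol 11.4.1.2 include both dose days, a 10-day gap spans 11 days and does not qualify. Gaps of 8 and 9 days span 9 and 10 and still do.

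**Weekly dosing.** Day 8 has no window and later doses have ±1 day. If the intermediate home doses are also counted from Day 1, the gap is 7 + y − x and reaches 5 days in 1 of 9 pairs from Week 2 onward. If both dose days count, 5 days spans 6 and no longer qualifies.

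**Effect on the primary endpoint.** Cmax and AUC are defined after the first dose. The next dose then follows at 13–15 days (q2w) or 7 days (weekly), so neither is touched. Core q2w trough samples are taken at Weeks 2, 4, 8 and 12 (Protocol 9.1.1). The gaps before Weeks 2 and 4 (13–15 and 11–17 days) always satisfy the 11-to-17-day rule. Only Weeks 8 and 12 can lose a sample because the preceding gap was short.

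The pair counts describe what the schedule permits. They are not probabilities.

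**The case against.** The best defence is that 8.1 means 14 ± 3 days from the previous dose. The Day 1 reference is written for visits, and 8.1 has its own sentence on the administration window. Both overdose thresholds equal the shortest gap under that reading, and the q2w trough limits of 11 to 17 days are 14 ± 3. Read this way there is no conflict. The intent is plausible, but no section states it, and sites doing q2w core dosing at visits are told in 6.3.1 and 10.1 to count from Day 1. The weekly trough limits of 5 to 9 days do not fit the previous-dose reading.

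It can also be said that the overdose note in 8.1, coming straight after the windows, works as a floor. Read together with 6.3.1 it would give exactly the rule proposed below. But it is a reporting definition and not a scheduling instruction, so a site would have to infer the floor.

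Two limits on the point stand in full. The event needs a late dose followed by an early one, and 8.1 keeps windows for exceptional circumstances. Short gaps would also not go unseen: SAP 2.4.3.1 summarizes time between doses, and Protocol 11.4.1.2 lists dosing irregularities.

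**Conclusion.** The point holds as a minor inconsistency in the dosing schedule. In-window q2w gaps of 9–10 days (Week 4 to 6) or 8–10 days (each later core interval) are permitted and fall under the overdose definition in 8.1. On the inclusive calendar-day reading of 11.4.1.2 only gaps of 8–9 days do. This rests on the Day 1 reference governing q2w core doses because they are given at visits; 8.1 itself does not say so.

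A reader might infer three stronger things that the documents do not support.

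- **That some percentage of patients will be overdosed.** No document gives the spread of visit days, so any percentage would come from an assumed one.
- **That the weekly regimen has the same conflict.** That needs home doses counted from Day 1, which is not stated, and it disappears on the inclusive reading.
- **That the primary pharmacokinetic analysis is biased.** At most a few Week 8 or Week 12 trough samples become ineligible because of scheduling; the first-dose measures are unaffected.

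The reporting effect is also small. An overdose is recorded only when suspected or notified, and SAP Table 4 takes the overdose event of special interest from a checkbox for symptomatic cases.

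**What to change.** Add one sentence to Protocol 8.1 and 6.3.1, and repeat it in 10.1: each dose must be given within its window counted from Day 1 and at least 11 days (q2w) or 6 days (weekly) after the previous dose.

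The rule requires y ≥ x − 3 (q2w) or y ≥ x − 1 (weekly), and it never closes a window. After the latest Week 4 dose (x = 2), 5 of 7 days remain at Week 6. After x = 3, 4 of 7 days remain at the next q2w visit. After x = 1 on weekly dosing, 2 of 3 days remain.

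Both limits should be kept. Counting only from the previous dose would let delays accumulate to 1 + 2 + 3 × 4 = 15 days by Week 12, against the ±3 days in 6.3.1.

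The cost is slightly less freedom to reschedule after a late visit, and the sentence has to be carried in an amendment with written ethics committee approval (Protocol 15). The rule protects trough eligibility only on the short side; gaps over 17 days stay possible. As an option, in-window gaps under 11 or 6 days already given could have their own line in the planned time-between-doses summary, to tell them apart from dosing errors. The overdose definition can stay as it is.

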8.2 NON-INVESTIGATIONAL MEDICINAL PRODUCT(S)

Not applicable.

8.3 BLINDING PROCEDURES

Not applicable.

8.4 METHOD OF ASSIGNING PATIENTS TO TREATMENT GROUP

The list of randomized treatment kit numbers will be generated centrally by Sanofi. The IMPs are packaged in accordance with this list. Patients will be assigned a treatment kit by an interactive voice response system (IVRS) or an interactive web response system (IWRS).

Patients who meet the entry criteria will be included and will be dispensed the treatment kits within 2 weight groups (Group A: ≥ 30 kg and ≤ 60 kg for patients enrolled during the dose-finding portion and ≥ 30 kg for patients enrolled during the second and the third portions; Group B: < 30 kg and ≥ 10 kg for all 3 portions).

- For the dose-finding and second portions, the planned ratio of enrollments for the 2 weight groups is 1:1.
- For the third portion, there is no pre-specified enrollment ratio for the 2 weight groups, but each weight group will be capped at 70% (ie, 20 patients). As a result, the most unbalanced enrollments by weight group possible would be 20 versus 8 patients in the third portion.

Patients who meet exclusion criteria may be rescreened once during the open screening period of the study. A different patient identification will be issued. There is no requirement for a waiting period between the screen failure and the rescreening. The IVRS/IWRS report will flag rescreened patients. Patients that are rescreened will be required to sign a new consent form (if the patient has reached the legal age) or by parents or legal guardians. Visit 1 procedures must be repeated (except chest X-ray).

At the Screening Visit 1 (Day-28 to D-1, up to 31 days), the site staff will contact the IVRS/IWRS to obtain a patient number for each patient who gives informed consent. Each patient will be allocated a patient number associated with the center and allocated in chronological order in each site.

At the Baseline Visit 2 (Week 0, Day 1), after confirming the patient is eligible for entry into the treatment period, the site staff will contact the IVRS/IWRS in order to receive the first treatment allocation kit number. To minimize the amount of blood withdrawn and the number of visits while maintaining the evaluation of the primary endpoint, for Group B (< 30 kg and ≥ 10 kg, lighter weight group), patients will be randomly assigned to sarilumab PK sampling schedule 1 or 2 (only applicable for patients in the the dose-finding and second portions) (see [Section 9.1.1](#) for the detailed sarilumab PK sampling schedule). At subsequent visits during the treatment period, the site staff will call IVRS to obtain the next treatment kit number. A confirmation fax/e-mail will be sent to the site after each assignment.

An included patient is defined as a patient who is registered and assigned a treatment kit number. The IMP will also be recorded and tracked on the center IMP inventory forms.

Details of the IVRS/IWRS procedures will be provided to sites in the IVRS/IWRS site manual.

8.5 PACKAGING AND LABELING

The IMP will be provided in patient treatment kits containing labeled vials. The content of the labeling is in accordance with the local regulatory specifications and requirements. One kit contains one vial. The patients will be provided sufficient kits until the next site visit. Additional treatment kits, to provide medication to patients under circumstances, such as a damaged kit, will be allocated by IVRS when a “replacement treatment call” is made to IVRS.

8.6 STORAGE CONDITIONS AND SHELF LIFE

The study medication should be kept refrigerated between 2°C and 8°C at the site or at home.

Investigators or other authorized persons (eg, pharmacists) are responsible for storing the IMP in a secure and safe place in accordance with local regulations, labeling specifications, policies, and procedures and providing proper storage instructions to patients.

Control of IMP storage condition, especially control of temperature (eg, refrigerated storage) and the information on in-use stability and instruction for handling the compounds provided by Sanofi should be managed according to the rules provided by the Sponsor.

The IMP may be supplied from the site to the patient via a sponsor-approved courier company where allowed by local regulations and approved by the patient.

8.7 RESPONSIBILITIES

The Investigator, the hospital pharmacist, or other personnel allowed to store and dispense the IMP will be responsible for ensuring that the IMP used in the clinical trial is securely maintained as specified by the Sponsor and in accordance with applicable regulatory requirements.

The IMP will be dispensed in accordance with the Investigator's prescription and it is the Investigator's responsibility to ensure that an accurate record of IMP issued and returned is maintained.

Any quality issue noticed with the receipt or use of an IMP (deficiency in condition, appearance, pertaining documentation, labeling, expiration date, etc) should be promptly notified to the Sponsor. Some deficiencies may be recorded through a complaint procedure.

A potential defect in the quality of IMP may be subject to initiation of a recall procedure by the Sponsor. In this case, the Investigator will be responsible for promptly addressing any request made by the Sponsor, in order to recall IMP and eliminate potential hazards.

Under no circumstances will the Investigator supply IMP to a third party allow the IMP to be used other than as directed by this clinical trial protocol, or dispose of IMP in any other manner.

